**Table 11 Dose Decrements for Pomalidomide**

Dose	Reduced Pomalidomide Doses		
	First Dose Reduction	Second Dose Reduction	Third Dose Reduction
4 mg	3 mg	2 mg	1 mg

If the dose of either the pomalidomide or oprozomib is reduced during the previous cycle, the reduced dose level will be continued on Day 1 of the next cycle. If the reduced dose level is well tolerated for a complete cycle, the subject may, at the investigator's discretion, be rechallenged with the dose level prior to the reduction at the start of the next cycle.

Treatment guidelines for specific hematologic toxicities are outlined in [Section 10.4.2.1.1](#) and nonhematologic toxicities in [Section 10.4.2.1.2](#). In addition to dose reductions, administration of oprozomib, pomalidomide, and dexamethasone may be temporarily interrupted for a maximum of 4 weeks in the event of a treatment-related toxicity. If the dose delay because of toxicity is longer than 4 weeks, the subject will be discontinued from study treatment. If a subject misses more than 4 consecutive weeks for reasons other than toxicity after completing Cycle 1, the subject will be discontinued from study treatment unless it is determined that the subject was benefiting from therapy and the **Sponsor's** study medical monitor permits the subject to resume therapy.

Dose reduction levels for dexamethasone are provided in [Table 12](#).

**Table 12 Dose Decrements for Dexamethasone**

Nominal Dose	Reduced Dexamethasone Doses	
	Dose -1	Dose -2
20 mg	12 mg	8 mg
Cycle 2 +: Age > 75 yrs per investigator discretion 10 mg	8 mg	4 mg

For subjects over 75 years old, after the first cycle and at the investigator's discretion, dexamethasone can be reduced to 10 mg. Dexamethasone will be permanently discontinued after 2 dose reductions for either nominal dose in the event of additional dexamethasone-related toxicity. At the investigator's discretion, dexamethasone may be

Approved

tapered prior to complete discontinuation according to institutional practice. If the dexamethasone dose is reduced during the previous cycle, the reduced dose level will be continued on Day 1 of the new cycle. If the reduced dose level is well tolerated for a complete cycle, the subject may, at the investigator's discretion, be rechallenged with the dose level prior to the reduction at the start of the next cycle.

If dexamethasone dosing is permanently stopped due to toxicity in accordance with the dose modification guidelines described in [Table 15](#), the subject should stay on oprozomib and/or pomalidomide, depending on the arm to which they are randomized, and continue to follow protocol required therapy, procedures, and assessments. Subjects may continue to take antiemetic doses of dexamethasone (4 mg) on days of oprozomib dosing, if tolerated, at the investigator's discretion.

#### ***10.4.2 DOSE MODIFICATION GUIDELINES***

##### **10.4.2.1 Oprozomib Dose Modification Guidelines**

###### **10.4.2.1.1 Hematologic Toxicities**

Dose modification guidelines for oprozomib/placebo and pomalidomide for hematologic toxicities are summarized in [Table 13](#).

Approved

**Table 13 Guidelines for Dose Modification of Oprozomib/Placebo and Pomalidomide for Hematologic Toxicities**

Findings	Oprozomib	Pomalidomide
Findings on Day 1 of Cycle		
Recommended Action		
Platelets $< 25 \times 10^9/L$	Hold dose a until recovery $\geq 25 \times 10^9/L$ ; restart at previous dose.	Not applicable.
Platelets $< 30 \times 10^9/L$	Not Applicable.	Hold dose a , follow CBCs. Hold prophylactic anticoagulation until platelets return to $\geq 30 \times 10^9/L^a$ , then resume at 1 dose decrement.
ANC $< 0.5 \times 10^9/L$ or febrile neutropenia (fever $\geq 38.5^\circ C$ and ANC $< 1.0 \times 10^9/L$ )	Hold dose a . Add colony stimulating factor b With resolution to $\geq 1.0 \times 10^9/L$ , restart at previous dose.	Hold dose a . Add colony stimulating factor b With resolution to $\geq 0.5 \times 10^9/L$ , restart at 1 dose decrement.
Findings on Subsequent Days of Cycle		
Recommended Action		
Platelets 25 to $< 50 \times 10^9/L$ without $\geq$ Grade 2 bleeding/hemorrhage	Full dose.	Full dose.
Platelets 25 to $< 50 \times 10^9/L$ with $\geq$ Grade 2 bleeding/hemorrhage	Hold dose a until platelets return to $\geq 50 \times 10^9/L$ and/or bleeding is controlled, then resume at 1 dose decrement.	Hold dose a until platelets return to $\geq 50 \times 10^9/L$ and/or bleeding is controlled, then resume at 1 dose decrement.
Platelets $< 25 \times 10^9/L$ or thrombocytopenia with $\geq$ Grade 2 bleeding/hemorrhage	Hold dose a until recovery to $\geq 25 \times 10^9/L$ ; restart at 1 dose decrement.	Hold dose a . Hold prophylactic anticoagulation until platelets return to $\geq 30 \times 10^9/L^a$ , then resume at 1 dose decrement.
Neutropenic fever (ANC $< 1.0 \times 10^9/L$ and single temperature $> 38.3^\circ C$ or temperature $> 38.0^\circ C$ sustained for more than 1 hour)	Hold dose a ; follow CBC at least 3 times per week. Add colony stimulating factor b With resolution of fever and ANC $\geq 1.0 \times 10^9/L$ , restart at 1 dose decrement.	Hold dose a ; follow CBCs. Add colony stimulating factor b . With resolution of fever and ANC $\geq 1.0 \times 10^9/L$ , restart at 1 dose decrement.
ANC $< 0.5 \times 10^9/L$	Hold dose a ; follow CBC at least 3 times per week; administration of colony stimulating factor b is permitted. Resume at full dose if ANC $\geq 0.5 \times 10^9/L$ within $< 7$ days. Resume at 1 dose decrement if ANC returns to $\geq 0.5 \times 10^9/L \geq 7$ days.	Hold dose a until ANC increases to $\geq 0.5 \times 10^9/L$ . Administer colony stimulating growth factor b . Resume at 1 dose decrement each subsequent decrease to $< 0.5 \times 10^9/L$ .

ANC = absolute neutrophil count; CBC = complete blood count.

a The maximum allowed dose interruption is 4 weeks for treatment-related toxicity.

b Colony stimulating factors such as filgrastim or sargramostim as examples.

Approved

Additional guidance regarding hematologic toxicities and dosing actions is as follows:

- To initiate a new cycle of pomalidomide, the neutrophil count must be at least 500 per  $\mu\text{L}$  and the platelet count must be at least 50,000 per  $\mu\text{L}$ . If toxicities continue to occur after dose reductions down to 1 mg, then discontinue pomalidomide.
- Nontreatment-related events: If the toxicity resolves to  $\leq$  Grade 1 or baseline and the toxicity is not treatment-related, oprozomib may be restarted at the same dose level
- If required by continued or recurrent toxicity, a second or third dose reduction of oprozomib may be permitted after discussion with the **Sponsor's** study medical monitor. No more than 3 dose reductions down to a minimum of 150 mg will be permitted for an individual subject on study and additional reductions will be managed by schedule change. If toxicity continues, oprozomib should be discontinued.

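### In Table 13, the Day 1 febrile neutropenia hold on pomalidomide can be met and released by the same neutrophil count, with no fever condition on restart, unlike the row for later days

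*Protocol*

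**What the plan says.** All the rules at issue are in Protocol Section 10.4.2.1.1, Table 13. ANC values below are in units of 10^9/L.

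The section on findings at Day 1 of a cycle has a single neutropenia row. It is triggered by ANC below 0.5, or by febrile neutropenia, given there as a temperature of at least 38.5 °C with ANC below 1.0. Both drugs are held and a colony stimulating factor is added. Pomalidomide then follows "With resolution to $\geq 0.5 \times 10^9/L$ , restart at 1 dose decrement". Oprozomib follows "With resolution to $\geq 1.0 \times 10^9/L$ , restart at previous dose". Neither instruction refers to fever.

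The section on subsequent days has a separate neutropenic fever row, triggered by ANC below 1.0 with "single temperature $> 38.3^\circ C$ or temperature $> 38.0^\circ C$ sustained for more than 1 hour". For both drugs the release condition is "With resolution of fever and ANC $\geq 1.0 \times 10^9/L$ , restart at 1 dose decrement".

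The guidance under the table sets a minimum of 500 neutrophils per µL for starting a new pomalidomide cycle. It does not mention fever either.

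**The concern.** A hold rule works only if the state that starts it fails the test that ends it. In the Day 1 row the pomalidomide release threshold (0.5) lies below the febrile trigger threshold (1.0), and the other half of the trigger, fever, is missing from the release. Read literally, the row lets some subjects resume pomalidomide while still febrile with the count that prompted the hold.

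The same clinical picture on another day falls under a stricter release test. How long a subject is off pomalidomide after febrile neutropenia can thus depend on the day it is found. That is first a safety matter. It also adds avoidable variation to the relative dose intensity that Protocol Section 14.4.1 plans to summarize.

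**Working it through.** The protocol gives no figure to reproduce; this is a comparison of conditions. The two febrile neutropenia rules in Table 13 are:

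| | Day 1 of cycle | Subsequent days |
|---|---|---|
| Temperature that counts | at least 38.5 °C | above 38.3 °C once, or above 38.0 °C for more than 1 hour |
| ANC that counts, with fever | below 1.0 | below 1.0 |
| Pomalidomide restart | ANC at least 0.5; fever not mentioned; 1 decrement | fever resolved and ANC at least 1.0; 1 decrement |
| Oprozomib restart | ANC at least 1.0; fever not mentioned; previous dose | fever resolved and ANC at least 1.0; 1 decrement |

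**1. Pomalidomide, Day 1.** The febrile hold covers ANC in [0, 1.0). Restart is allowed for ANC in [0.5, ∞). The intersection is [0.5, 1.0). A subject with 38.6 °C and ANC 0.7 is held and meets the restart condition at once. If the word resolution is taken to presuppose a count that began below 0.5, this subject has no restart rule at all, which is also a defect.

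**2. Pomalidomide, later days.** The hold covers [0, 1.0) and restart needs [1.0, ∞), so the intersection is empty. Fever must also have gone. The same subject stays on hold.

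**3. Febrile with ANC below 0.5.** On Day 1 the count must rise to 0.5, so release is not immediate. The remaining differences are the later-day requirements for ANC of at least 1.0 and no fever.

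**4. Oprozomib, Day 1.** The hold [0, 1.0) and restart [1.0, ∞) do not overlap. Fever is still not addressed, so a subject whose count reaches 1.0 while febrile meets the restart condition.

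**5. Fever definitions.** A single reading of 38.4 °C with ANC 0.7 meets the later-day trigger (38.4 > 38.3) but not the Day 1 trigger (38.4 < 38.5).

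**6. Does other text close the gap?**
- New-cycle minimum under Table 13: 500 per µL equals 0.5 × 10^9/L, the same threshold, again without fever.
- Table 14, infection row: holds both drugs until systemic treatment is complete, but only for Grade 3 or 4 infection, and it sends subjects with ANC below 1.0 back to Table 13.
- Section 10.4: written exceptions may be approved by the medical monitor, but this sets no rule.
- Section 10.4.1: a dose already reduced in one cycle carries into Day 1 of the next. This does not settle which row governs a subject still on hold, with no reduced dose yet given, when the cycle turns.
- Section 10.4.1 also says pomalidomide adjustments generally follow the prescribing information. That source is not available here, and the protocol does not say that it overrides an explicit Table 13 instruction.

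**7. When it applies.** Entry requires ANC of at least 1500/mm³, or 1.5 × 10^9/L (Section 6.1), and Day 1 of Cycle 1 precedes treatment. In practice the row matters from Cycle 2.

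**8. Size.** Section 3.5.3 reports febrile neutropenia in 1 subject in each of two age groups (2%) in the randomized Phase 2 study of pomalidomide with low-dose dexamethasone. Applied to the planned 82 subjects for illustration: 82 × 0.02 = 1.64 subjects with any febrile neutropenia. Those found on Day 1 with ANC from 0.5 to below 1.0 are a subset. The rate with oprozomib added is not given and could be higher.

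**The case against.** The best defence is that Table 13 deliberately treats Day 1 and later days differently. The platelet rows show it: below 25 × 10^9/L on Day 1, oprozomib restarts at the previous dose; on later days it restarts one decrement lower. A reader might infer that the differing oprozomib restart dose after febrile neutropenia is itself a contradiction. The platelet pattern does not support that, and the point does not rest on it. For afebrile subjects, 0.5 is also the consistent pomalidomide threshold: Day 1, later days and the new-cycle rule all use it.

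Other strong readings fail as well:
- That the Day 1 row governs most cases, because from Cycle 3 scheduled counts fall on Day 1. Fever can occur on any day, and Section 11.2 allows unscheduled samples for managing adverse events or dose modification.
- That the rule bears materially on the DLT endpoint. Treatment-related febrile neutropenia within Cycle 1 arises after Day 1, where the stricter row applies. A Cycle 2 start delayed beyond 14 days is a DLT, but nothing in the documents shows that this row would often decide such a delay.
- That the 41% to 42% Grade 3 or 4 neutropenia quoted in Section 3.5.3 measures the problem. The relevant figure there is the 2% febrile rate.
- That both drugs may restart while ANC is below 1.0. That is true of pomalidomide only.

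The actions are also headed as recommended, and a clinician might well keep a febrile subject on hold. None of this explains a release condition that the triggering count already meets. An intended Day 1 distinction does not require it, and the same table states fever explicitly where it is wanted.

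**Conclusion.** The point holds for the Day 1 febrile neutropenia row. For ANC from 0.5 to below 1.0, the pomalidomide hold and release conditions are met together, with fever unaddressed; the later-day row has no such overlap. Two related inconsistencies stand: the missing fever condition for oprozomib on Day 1, and the different temperature definitions. The pomalidomide restart is one decrement in both febrile rows, so for that drug the difference lies in when dosing may resume, not in the resumed dose.

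The number of subjects affected is probably small. That judgement assumes the 2% background rate is a fair guide, although it comes from treatment without oprozomib. The matter is still worth correcting, because it is a safety rule that fails as written. A reader might go further and infer that each event must have one restart rule whatever the day. The documents do not support that: a Day 1 distinction may be intended.

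**What to change.** Reconcile three items in Table 13: the Day 1 febrile neutropenia trigger, its restart conditions for both drugs, and the neutropenic fever row for subsequent days. The result should be that the condition starting a hold cannot also satisfy its release, that the role of fever in restarting is stated, and that the fever definitions agree or their difference is explained. Add a sentence saying which row applies to an episode found mid-cycle and still present on the next Day 1.

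The thresholds, the doses, and whether Day 1 and later-day actions should differ are clinical decisions for the sponsor. The cost is wording in one table, with no effect on sample size or planned analyses.

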**Table 14 Guidelines for Dose Modification of Oprozomib/Placebo and Pomalidomide for Nonhematologic Toxicities (cont'd)**

Symptom	Findings	Recommended Action a	
		Oprozomib	Pomalidomide
Renal Dysfunction	CrCl 30 to < 50 mL/min (Grade 2)	Full dose.	Full dose.
	CrCl 15 to < 30 mL/min (Grade 3)	Hold dose. When CrCl recovers to ≤ Grade 2, resume at 1 dose decrement.	Hold dose. When CrCl recovers to ≤ Grade 2, resume dose at 1 dose decrement. If Grade 3 CrCl reappears, then hold dose until CrCl recovers to ≤ Grade 2 and reduce dose an additional 1 dose decrement.
	CrCl 0 to < 15 mL/min (Grade 4)	Discontinue.	Discontinue.
Elevation in Liver Function Tests	≥ Grade 3 (AST, ALT, or total bilirubin) b	Hold until resolves to baseline. Resume at 1 dose decrement.	Hold pomalidomide and restart treatment at 1 dose decrement less than the previous dose when toxicity has resolved to ≤ Grade 2 at physician discretion.
Other Nonhematologic Toxicity	Assessed as oprozomib-related and ≥ Grade 3 c	Hold oprozomib dose until toxicity resolves to ≤ Grade 1 or baseline; restart at 1 dose decrement.	Full dose.
Other Nonhematologic Toxicity	Assessed as pomalidomide-related and ≥ Grade 3 e,d	Full dose.	Hold pomalidomide and restart treatment at 1 dose decrement less than the previous dose when toxicity has resolved to ≤ Grade 2 at physician discretion.
Grade 1 or 2 GI hemorrhage	Assessed as oprozomib-related	DELAY until Grade 0 DECREASE one dose level for Grade 2	Full dose at physician discretion
Grade 3 or 4 GI Hemorrhage	Assessed as oprozomib-related	Discontinue.	Full dose when AE resolves to ≤ Grade 2 at physician discretion.

5-HT3 = 5-hydroxytryptamine type-3; AE = adverse event; ALT = alanine aminotransferase; ANC = absolute neutrophil count; AST = aspartate aminotransferase; CrCl = creatinine clearance; eCRF = electronic case report form; GI = gastrointestinal; LDH = lactate dehydrogenase; ULN = upper limit of normal.

a The maximum allowed dose interruption is 4 weeks for treatment-related toxicity.

b If AST or ALT is ≥ 3 × ULN, the “evaluation of treatment emergent liver abnormalities” eCRF should be completed.

c If cardiac or pulmonary treatment-emergent toxicities occur, the “cardiopulmonary AE” eCRF should be completed.

d See [Celgene Corporation, 2013](#).

Approved

Additional guidance regarding nonhematologic toxicities and dosing actions is as follows:

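### Table 13's below-25 platelet row sets restart counts with no bleeding condition, so read literally it permits a mid-cycle restart where the adjacent row says hold

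*Protocol*

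**What the plan says.** Section 10.4.2.1.1 of the protocol sets the platelet rules in Table 13. Two adjacent rows under the subsequent-days heading matter here. Counts are in units of 10⁹/L.

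- **The 25-to-50 row** applies to counts of 25 to below 50 with bleeding of Grade 2 or worse. Both drugs are held "until platelets return to $\geq 50 \times 10^9/L$ and/or bleeding is controlled, then resume at 1 dose decrement".
- **The below-25 row** applies to counts below 25 "or thrombocytopenia with $\geq$ Grade 2 bleeding/hemorrhage". Oprozomib is held "until recovery to $\geq 25 \times 10^9/L$ ; restart at 1 dose decrement". The pomalidomide cell says to hold the dose and continues: "Hold prophylactic anticoagulation until platelets return to $\geq 30 \times 10^9/L^a$ , then resume at 1 dose decrement".

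The notes after the table say that, to start a new pomalidomide cycle, "the platelet count must be at least 50,000 per" microlitre. They do not say which row takes precedence.

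Three other provisions bear on the same situation:

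- Section 10.4.1 says that all three drugs "may be temporarily interrupted for a maximum of 4 weeks in the event of a treatment-related toxicity".
- For oprozomib-related gastrointestinal hemorrhage of Grade 1 or 2, Table 14 tells the site to "DELAY until Grade 0 DECREASE one dose level for Grade 2". At Grade 3 or 4 oprozomib is discontinued.
- For other oprozomib-related nonhematologic toxicity of Grade 3 or worse, Table 14 says "Hold oprozomib dose until toxicity resolves to ≤ Grade 1 or baseline; restart at 1 dose decrement".

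**The concern.** The two rows can describe the same subject, or the same subject a few days apart, and they give different restart conditions. The row written for the lower count has the looser rule: it looks only at platelets, although active bleeding is one of the findings that brings a subject into it. Two sites could manage the same bleeding subject differently and both be within the table.

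Bleeding is a known hazard here. Section 3.4.2.2 reports two fatal gastrointestinal bleeds on oprozomib, and Section 3.4.2.3 reports a subarachnoid hemorrhage as a DLT with oprozomib plus dexamethasone. Section 10.6.1.6 requires aspirin or another antithrombotic while pomalidomide is taken. What is at stake is restarting study drug during an uncontrolled bleed with a low platelet count.

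**Working it through.** No statistical calculation applies. The check compares the two rows for a subject whose bleeding is Grade 2 or worse and not controlled.

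**Step 1: do the rows overlap?** The second limb of the below-25 row asks only for thrombocytopenia with such bleeding and gives no count. A subject at 25 to below 50 with such bleeding therefore meets both rows. Reading that limb as counts below 25 would make it redundant, because the first limb already covers every count below 25.

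**Step 2: what does each row say while bleeding continues?**

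| Platelets (× 10⁹/L) | 25-to-50 row | Below-25 row, oprozomib (25) | Below-25 row, pomalidomide (30) |
|---|---|---|---|
| below 25 | does not apply | hold | hold |
| 25 to below 30 | hold both drugs | count met | count not met |
| 30 to below 50 | hold both drugs | count met | count met |

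The hold in the 25-to-50 row does not depend on how its *and/or* is read. Below 50 with bleeding uncontrolled, neither condition is satisfied.

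**Step 3: what if the below-25 row is confined to counts below 25?** Take a subject at 20 with a Grade 2 bleed. Only the below-25 row applies. When the count reaches 25, that row's oprozomib condition is met whether or not bleeding has stopped, yet the subject now fits the 25-to-50 row, which says hold. The conflict survives the narrower reading.

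**Step 4: what do other provisions remove?**

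- *Gastrointestinal bleeding.* Table 14's hemorrhage rows cover oprozomib-related events.
- *Grade 3 or worse.* Table 14's general oprozomib row holds the drug until Grade 1 or baseline. Its general rows start at Grade 3, so Grade 2 non-gastrointestinal bleeding falls outside them.
- *New pomalidomide cycle.* 50,000 per microlitre × 10⁶ microlitres per litre = 50 × 10⁹/L. A pomalidomide restart at 30 to below 50 can therefore only be mid-cycle.
- *General interruption.* Section 10.4.1 allows a hold but gives no restart criterion, so it does not choose between the rows.

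**Step 5: does the table state joint conditions elsewhere?** Yes. The neutropenic-fever row for subsequent days requires both resolution of fever and neutrophil recovery to 1.0 × 10⁹/L. A clinical condition joined to a count is already within the table's style.

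**The case against.** The strongest reply is that ordinary reading settles the matter. The below-25 row speaks of recovery to 25 and return to 30, words that suit a subject who began lower. A subject at 40 cannot recover to 25, and the 25-to-50 row names that subject's state exactly. A subject who climbs from below 25 to 25 while bleeding then shows the finding in the 25-to-50 row, and re-reading the table gives a hold. This makes the conflict less stark, and it is why the recovering subject is a better example than the subject at 40. It does not remove the conflict: the below-25 row still gives an explicit restart instruction at 25, and nothing says to re-enter the table at the other row.

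Second, the count of 30 in the pomalidomide cell is attached grammatically to anticoagulation. That is fair. The closing words about resuming at a dose decrement make 30 the natural pomalidomide restart count, but this is a reading. On the other reading the cell gives pomalidomide no restart count, and still no bleeding condition.

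Third, these are headed as recommended actions, Section 10.4.1 lets the investigator keep holding, and Section 10.4 allows exceptions with the medical monitor's written approval. All of that stands. A reader might infer that the table compels dosing during a bleed; it does not. Equally, a site that follows the below-25 row literally needs no exception, so the approval step would not catch it.

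Fourth, the protocol's opening note says the program was terminated and Amendment 3 was not implemented. That limits remaining exposure without making the table consistent. The Amendment 3 summary of changes lists no revision to Table 13.

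**Conclusion.** The inconsistency is real and small. Read literally, the below-25 row permits a mid-cycle restart below 50 × 10⁹/L during uncontrolled bleeding of Grade 2 or worse, where its neighbor says hold. The clearest exposed case is Grade 2, non-gastrointestinal bleeding in a subject recovering from below 25. The conclusion rests on the absence of any precedence rule and, for pomalidomide, on reading 30 as that drug's restart count.

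Three stronger inferences are not supported:

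- The rows do not disagree on the restart dose; both use one decrement.
- Nothing here shows an effect on DLT counts or the MTD.
- Exposure cannot be gauged by counting scheduled blood counts, because Section 11.2 allows unscheduled samples for managing adverse events or dose changes. The number of subjects affected is unknown.

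This is a minor safety clarification.

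**What to change.** Make three wording changes to Table 13:

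1. Limit the below-25 row to platelets below 25 × 10⁹/L.
2. In both drug cells of that row, add that when bleeding of Grade 2 or worse is present, restart also requires the bleeding to be controlled.
3. State that a subject at 25 to below 50 with such bleeding, including one recovering from below 25, follows the 25-to-50 row.

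Gastrointestinal hemorrhage continues to follow Table 14. The platelet cut-offs are a matter for the sponsor's medical team.

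It is tempting to add a rule for bleeding at counts of 50 or more. That should be done only if the *and/or* in the 25-to-50 row is settled at the same time, for example by requiring bleeding control in every case. Read as *or*, that row lets a subject who reaches 50 resume while still bleeding, and a separate hold at 50 or above would create a new contradiction.

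The cost is table text and, where the protocol or a successor is in use, a notice to sites. No visits, data or subjects are added. The downside is an occasional longer hold within the existing 4-week maximum.
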